Patients should be advised to take study medication with a full glass of water. Breaking or chewing of the tablets or capsules, or emptying the contents of the capsules is not permitted. The capsules and tablets should be swallowed as a whole and should not be dissolved in liquid. It is possible to take study medication with or without food. By taking study medication with food, dyspepsia-like side effects associated with DE may be reduced ([U13-3509-01](#)). If dyspeptic symptoms remain, the Investigator should consider adding a proton pump-inhibitor or H2-blocker to the concomitant therapy of the patient.

Start of study treatment following the qualifying event of ESUS:

The decision about starting study medication after qualifying stroke is at the discretion of the Investigator. In general, study medication should be started as early as possible under consideration of the severity of the stroke and after ensuring that intracranial hemorrhage has been excluded. Recommendations on the earliest possible time point to start study medication are provided in [Table 4.1.4: 1 \(P12-02400\)](#).

Table 4.1.4: 1 Recommendations on starting study medication after index event of stroke (mRS \leq 3 at time of randomization) and for reintroduction of study treatment after recurrent stroke (mRS \leq 3 at time of study medication restart)

Stroke Severity (at time of randomization / at time of study medication restart after recurrent stroke)	Earliest start of Study Medication after Stroke
Symptom resolution within 24 hours with evidence of brain damage by imaging	As soon as imaging has excluded a cerebral hemorrhage
Modified Rankin Scale = 1 or 2	3-5 days after most recent stroke onset ¹ Brain re-imaging is not required if starting study medication more than 10 days after index stroke.

Modified Rankin Scale = 3
 
Please take note:
 
This category includes patients with an initial Modified Rankin Scale of 4 at time of stroke, who have improved to a Modified Rankin Scale of 3.
 
Patients with Modified Rankin Scale of 4 at time of randomization are excluded.
 
Patients with Modified Rankin Scale of 4 cannot restart study medication unless their Modified Rankin Scale improves to 3.
	
5-7 days after most recent stroke onset¹
 
Brain re-imaging is not required if starting study medication more than 10 days after index stroke.

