¹ If starting study medication within 10 days of most recent stroke in patients with mRS of 1, 2, or 3, re-imaging of the brain is required to rule out bleeding into the brain. Randomization in these patients should only occur after reimaging of the brain has been performed and eligibility has been confirmed. Hemorrhagic transformation of a primarily ischemic stroke may be included as per Investigator's judgment. Sporadic microbleeds may be included as per Investigator's judgment. As a general recommendation, a cerebral microbleed is considered to be in general \leq 5mm, but sometimes up to 10 mm, in greatest diameter on gradient recalled echo (GRE), or T2*, MRI sequences. Microbleeds are incidental findings that do not constitute an exclusion criterion. In patients with hemorrhagic transformation or microbleeds, the Investigator may choose to delay the start of study medication. Any blood visualized on a CT will be classified as a macrobleed. In patients with macrobleeds, study medication should not be started.

Treatment will continue until the end of the study if there is no reason to stop treatment earlier. The date of last dose of study drug will be recorded on the eCRF.

Secondary stroke prevention treatment for patients after the completion of this trial is at the discretion of the Investigator or other treating physician.

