As study medication is blinded, the following characteristics of ASA should also be taken into consideration for the management of bleeding (adapted from [P10-03790](#)):

There is no specific reversal agent to counteract the antithrombotic activity of ASA. Since ASA is renally excreted adequate diuresis must be maintained. Alkalinization of the urine is a

key concept in the management of salicylate overdose (see “Overdose” later within this section).

Re-administration of study medication after a major bleed

Re-administration of study medication (at the assigned dose) after the bleeding has resolved and hemostasis has been achieved, is at the discretion of the local Investigator.

Minor Bleeds

If a patient experiences a minor bleed, study medication may be continued, interrupted temporarily or permanently discontinued, at the discretion of the Investigator. It is not a requirement however, that study drug is stopped in these cases.

Stroke

Patients with documented or suspected stroke should be managed according to usual clinical practice, which may include the use of fibrinolytic agents and mechanical clot removal. It is anticipated that in most cases study drug will be withheld until a CT or MRI scan has been obtained.

Ischemic stroke

For ischemic stroke, ASA and/or clopidogrel, or ASA/dipyridamole (the latter in lieu of clopidogrel) may be administered as indicated according to usual clinical practice. Treatment with study drug can be continued at the discretion of the local Investigator, in the absence of evidence of bleeding. For recommendations on timing of restart of study medication see below in section “*reintroduction of study treatment following a stroke*”, see [Table 4.1.4: 1](#).

Use of fibrinolytic agents for the treatment of acute ischemic stroke:

The use of fibrinolytic agents for the treatment of acute ischemic stroke may be considered if the patient presents with a TT, dTT, ECT, or (if TT, dTT or ECT are not available) an aPTT lab result not exceeding the ULN according to the local reference range. Either TT or dTT, ECT (one of these parameters is preferred), or aPTT will be sufficient and the choice of the parameter will depend on local availability) ([U11-1642-01](#)).

Refer to [Section 4.1.5.2](#) for Emergency Unblinding Procedures.

Hemorrhagic Stroke

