For hemorrhagic stroke or other intracranial bleeding, consultation with a coagulation expert and a neurosurgeon is recommended. See “Major Bleeds” earlier in this section for details relating to how to manage bleeding.

In case of recurrent stroke during the trial, it is at the Investigator's discretion whether study medication will be restarted or whether the patients will be switched to appropriate standard of care antithrombotic treatment.

Reintroduction of study treatment following a stroke (i.e. after recurrent stroke)

The decision about when to restart study medication following a recurrent stroke is at the discretion of the Investigator (with the exception of strokes with mRS of 4 or higher, where restart is not allowed, unless the patient improves to a mRS of 3). [Table 4.1.4: 1](#) shows recommendations ([P12-02400](#)) on the earliest possible time point to start study medication. These recommendations in [Table 4.1.4: 1](#) also apply to restarting study medication after recurrent stroke. Cerebral hemorrhage must be excluded before study drug is restarted. If restarting study medication within 10 days of stroke in patients with mRS of 1, 2 or 3, re-imaging is required to rule out bleeding into the brain (for details see footnote of [Table 4.1.4: 1](#)).

Acute Coronary Syndrome (ACS)

In patients with documented or suspected ACS, study drug should be temporarily discontinued.

Medication Management of ACS

ASA, clopidogrel and glycoprotein IIb/IIIa inhibitors may be administered according to usual clinical practice. However, the concomitant use of these treatments with study medication may increase the risk of bleeding.

For the use of heparins (UFH or LMWH) or other anticoagulants to manage ACS, the following guidance is provided for consideration:

Unfractionated or low-molecular-weight heparin should be withheld until the aPTT is less than 1.5 x ULN (upper limit of normal):

- If the aPTT is between 1.2 and 1.5 x ULN, UF heparin may be commenced preferably without an intravenous loading dose and LMWH may be commenced at the usual therapeutic dose
- If the aPTT is above 1.5 times the ULN, it should be repeated every four hours until it falls below this level, after which heparin or other anticoagulation can be commenced.

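### Protocol 4.2.1 lets study drug be continued after a recurrent ischemic stroke without the mRS limit and repeat scan that a restart requires

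*Protocol*

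**What the plan says.** Protocol 4.2.1 treats stroke under several sub-headings.

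- *Stroke*: "It is anticipated that in most cases study drug will be withheld until a CT or MRI scan has been obtained".
- *Ischemic stroke*: "Treatment with study drug can be continued at the discretion of the local Investigator, in the absence of evidence of bleeding". The next sentence points to the advice on when to restart.
- *Reintroduction of study treatment following a stroke*: the investigator decides when to restart, except for "strokes with mRS of 4 or higher, where restart is not allowed, unless the patient improves to a mRS of 3". In addition, "Cerebral hemorrhage must be excluded before study drug is restarted", and "If restarting study medication within 10 days of stroke in patients with mRS of 1, 2 or 3, re-imaging is required" to rule out bleeding.

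Table 4.1.4: 1 repeats the mRS 4 limit for restart. Its footnote 1 opens the re-imaging rule with "If starting study medication within 10 days of most recent stroke in patients with mRS of 1, 2, or 3". The recommended earliest times are 3-5 days at mRS 1 or 2 and 5-7 days at mRS 3. Where symptoms resolve within 24 hours, drug may be given "As soon as imaging has excluded a cerebral hemorrhage".

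The mandatory reasons for stopping drug in Protocol 3.3.4.1 are a new antithrombotic indication (including atrial fibrillation), creatinine clearance below 30 mL/min, noncompliance, pregnancy and withdrawn consent. Neither a recurrent stroke nor a level of disability is on that list.

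**The concern.** Protocol 2.3 gives the reasons for the safeguards. Patients at mRS 4 or higher are kept out because a large infarct may bleed under an anticoagulant. Early re-imaging is there to find bleeding that the scan at stroke onset missed. Both reasons apply at least as strongly to a patient who stays on blinded drug, possibly dabigatran, through a new infarct. That patient is exposed sooner than one who stops and restarts.

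As worded, the patient with the earlier exposure faces fewer mandatory checks. A patient at mRS 2 who restarts on day 9 must have a repeat scan; a patient at mRS 2 who never stopped need not. A patient at mRS 4 may not restart, but no rule says that the same patient may not continue. With approximately 550 planned sites (Protocol 3.3), practice could differ from site to site.

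**Working it through.** No formula governs the main point. The check asks whether each rule binds a patient whose drug is never interrupted.

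| Rule | Place | Act it governs | Binds a patient who never stops? |
|---|---|---|---|
| No drug at mRS 4 or higher | 4.2.1 Reintroduction; Table 4.1.4: 1 | Restart | No |
| Repeat scan within 10 days at mRS 1-3 | 4.2.1 Reintroduction; Table 4.1.4: 1 footnote 1 | Restart; start | No |
| Hemorrhage excluded | 4.2.1 Reintroduction | Restart | Not by this rule; the continuation sentence has its own, weaker condition |
| Hold until CT or MRI | 4.2.1 Stroke | Stated as an expectation | No |
| Mandatory stop list | 3.3.4.1 | Stopping | No matching trigger |
| Stop in the patient's interest | 3.3.4.1 | Stopping, optional | Allows it, does not require it |
| Stop for a major bleed | 4.2.1 Major Bleeds | Stopping | Yes, but only once the bleed is known |
| Important violation C3.1 | SAP Table 6.2: 1 | Failure to interrupt | Names only atrial fibrillation and creatinine clearance below 30 |

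Flow Chart footnote 19 does not help: its repeat-scan rule concerns initiation after the index event.

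**Does 'continued' mean without a break?** Minor Bleeds, in the same section, uses the word as the alternative to a pause: "study medication may be continued, interrupted temporarily or permanently discontinued, at the discretion of the Investigator". For acute coronary syndrome and for major bleeds, 4.2.1 directs that study drug be stopped, temporarily in the first case. Ischemic stroke has no such instruction.

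**Reach.** Only a loose ceiling can be formed.

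- Planned strokes: 353 (Protocol 3.1 and 7.6).
- Ischemic share: not given; assumed 80-100%.
- Both arms: 353 × 0.80 = 282 to 353 × 1.00 = 353.
- Dabigatran arm, taking the planned hazard ratio of 0.70, 1:1 allocation and events roughly proportional to hazard: 353 × 0.70 / 1.70 = 145. With the same assumed share: 145 × 0.80 = 116 to 145.

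Four groups must then be removed: patients already off drug, those held for imaging, those given a non-study antiplatelet, and those whose symptoms resolved within 24 hours. For the last group, the table's first row asks only that imaging exclude hemorrhage. The documents give no frequency for any of these groups, so the number actually affected cannot be calculated.

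**The case against.** The strongest reply is that 'continued' means staying in the trial regimen after a pause.

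- Just before the Reintroduction text, 4.2.1 gives the investigator two choices after a recurrent stroke: restart study medication or switch to standard care. Uninterrupted dosing is not a third.
- The sentence after the permission refers to restart, and the earliest times in Table 4.1.4: 1 presuppose an interruption.
- Minor Bleeds adds that stopping is not required. The stroke text does not, so the comparison of wording can be turned around.

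This makes interruption the likely intent. It does not settle the matter, because holding the drug is only expected, and only in most cases.

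Three stronger readings are tempting, and the documents do not support them.

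1. *A continuing patient has no hemorrhage safeguard.* The permission itself requires no evidence of bleeding, calling a stroke ischemic ordinarily needs a scan, and a recognised major bleed stops study drug. The safeguard is weaker than for restart, not absent.
2. *The section allows study drug together with clopidogrel or commercial aspirin after a stroke.* Protocol 4.2.2.1 and Appendix 10.2.1 bar that combination, and 3.3.4.1 stops drug for dual antiplatelet therapy. A patient given these agents must therefore interrupt, so any return is a restart under all the rules. This shrinks the gap further.
3. *Several hundred patients are exposed.* The 282-353 range counts planned ischemic strokes in both arms under an assumed share. It does not count patients who continue.

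**Conclusion.** The point holds in a limited form. Two safeguards, the mRS limit and the early repeat scan, are not worded to bind a patient who continues without interruption, and no other rule fills the space. Hemorrhage exclusion is only partly affected. The gap is confined to patients at mRS 1 or higher who are still on study drug, are not held for imaging and receive no acute non-study antiplatelet. Their number is unknown and probably small.

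The consequence is for patient safety and uniform conduct. The primary endpoint is time to first recurrent stroke, analyzed in all randomized patients over full follow-up, so what happens to study drug after that stroke does not alter the primary test or its power. The conclusion rests on the literal wording. If the sponsor always intended an interruption, the correction simply states that intent. It is worth making because a written permission conflicts with the protocol's own safety reasoning.

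**What to change.** In Protocol 4.2.1, Ischemic stroke, replace the permission to continue with:

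> Study drug should be withheld after a suspected or confirmed recurrent stroke. It may be resumed at the Investigator's discretion only under the restart rules below: cerebral hemorrhage excluded by imaging, mRS ≤3, and, if resumed within 10 days at mRS 1-3, re-imaging completed before the first dose.

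Placing the scan before the first dose matters: a rule that merely required re-imaging within 10 days would let dosing go on while the scan was awaited. Keep the times in Table 4.1.4: 1 as recommendations, including the row for symptoms that resolve within 24 hours. A cross-reference to 4.2.2.1 would make the antiplatelet restriction visible here. Sections 3.3.4.1 and 4.2.2.1 and the SAP need no change.

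The cost is one replaced sentence in an amendment. Patients who would have continued get a short interruption and, in some cases, a repeat scan of the kind already required for restart. Investigators lose a little discretion. No new data item is needed, since mRS at onset of a recurrent stroke is already assessed (Protocol 5.1.2.1).
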